4 TRIAL DESIGN

This is a double-blind, randomised, placebo-controlled, dose-ascending study to evaluate the safety, tolerability and immunogenicity of Vaccine FP-02.2 in HBeAg-negative hepatitis B patients as an add-on treatment to entecavir or tenofovir.

Actively treated subjects will receive either a Low or High dose of Vaccine FP-02.2 with or without IC31®.

A placebo arm is included in the study. Safety and immunogenicity data generated from the placebo arm will allow comparison to data generated from the Vaccine FP-02.2 High and Low dose study arms. The placebo group is also necessary to understand the rate of natural HBsAg seroconversion in an untreated study arm. An IC31® alone arm is included in the study which will additionally allow comparison of safety and immunogenicity data with data generated from the Vaccine FP-02.2 High and Low dose/IC31® study arms.

Approximately of 60 subjects (excluding replacements for subjects deemed ineligible after dosing) will complete this trial and will be assigned equally to 6 study arms (approximately 10/study arm).

Screening will occur up to 28 days prior to the first injection.

Up to 3 days before the first injection, eligible subjects will be randomised to treatment arm as shown in Table 2, depending on the cohort.

Subjects will receive 3 injections at intervals of 28 days (Day 1, Day 29, and Day 57). On the days of the injections the subjects will stay in the clinic for at least 4 hours after the first injection and 2 hours after the second and third injections and be monitored closely including an assessment of local reactions at the injection site. Approximately 24 hours after the first injection, the subjects will be asked to attend the clinic for safety assessments. For subsequent injections, subjects will receive a telephone call approximately 24 hours after each injection for safety follow-up. The subjects will be asked to return to the clinic 7 days after each injection for further assessments as well as 28 days after the last injection (Day 85). A follow-up visit will be performed 6 months after the end of the treatment period (i.e. 6 months after the last dose).

The first cohort starts with a low dose of Vaccine FP-02.2, 150µg/peptide (1350µg total peptide or placebo). The next cohort receives a higher dose of Vaccine FP-02.2, 500µg/peptide (4500µg total peptide) or a low dose of Vaccine FP-02.2, 150µg/peptide, in conjunction with 500nmol/20nmol KLK/ODN1a IC31® or placebo or 500nmol/20nmol KLK/ODN1a IC31® alone. The final cohort will test the high dose of Vaccine FP-02.2, in conjunction with 500 nmol/20 nmol KLK/ODN1a IC31® or 500nmol/20nmol KLK/ODN1a IC31® alone. See Table 2.

For each cohort, dosing will start with a sentinel group consisting of one subject from each treatment arm, receiving active or control (FP-02.2 (IC31®), IC31® or placebo), e.g. for Cohort 1, the sentinel group will consist of 1 subject receiving placebo and 1 subject receiving Low-dose Vaccine FP-02.2. After the assessments on Day 8, the SRC will meet and review the safety data from the sentinel group and recommend whether or not the remaining subjects of a cohort should be dosed. Any PI with patients in the sentinel group will provide input to the SRC meeting.

In order to progress to the next cohort, the SRC with input from the Investigators contributing patients will meet to review safety data up to Day 36 from Cohort 1. Following this review subjects may be dosed in Cohort 2 assuming the SRC has identified no safety concerns. Similarly, subjects may be dosed in Cohort 3 after review of safety data up to and including Day 36 from subjects in Cohort 2.

5 STUDY SETTING

This is a multi-national, multi-centre clinical trial and each site is responsible for recruitment, treatment, follow-up and continuing care for subjects enrolled in each site.

The study sites were selected based on their large cohorts of patients with HBeAg-negative chronic HBV infection and appropriate experience in clinical trials.

6 ELIGIBILITY CRITERIA

6.1 Inclusion criteria

1. Male and female subjects aged 18-65 years.
2. Diagnosed with CHB defined as HBsAg positive for at least 24 months.
3. Subject has received entecavir or tenofovir for at least 2 years with a stable dose for at least 6 months prior to screening.
4. HBeAg negative for at least 2 years prior to inclusion in the study.
5. HBV DNA <50 IU/mL for \geq 12 months
6. ALT or AST \leq 1.5 x the ULN via the local laboratory at the Screening Visit
7. Able to give written informed consent to participate
8. Females should fulfil one of the following criteria:
 - a. At least one year menopausal
 - b. Surgically sterile
 - c. Same-sex relationship
 - d. Women of childbearing potential not surgically sterilised or with laboratory confirmed menopausal status are required to use a highly effective contraceptive measure with low used dependency such as:
 - o Combined (oestrogen- and progestogen-containing) hormonal contraception associated with inhibition of ovulation
 - o Progestogen-only hormonal contraception implants associated with inhibition of ovulation
 - o Intrauterine device (IUD)
 - o Intrauterine hormone-releasing system (IUS)
 - o Bilateral tubal occlusion
 - o Vasectomised partner – must have had medical assessment of successful surgery.

From screening until one menstrual cycle after the last dose of IMP (Day 57).

Subjects who practice true abstinence or who exclusively have same sex partners need not use contraception, provided it is in line with their preferred and usual lifestyle. Periodic abstinence (eg, calendar, ovulation, symptothermal, post-ovulation methods) and withdrawal are not acceptable methods of contraception. Should any such subject stop practicing true abstinence, they must use contraception as described above.

Males should fulfil one of the following criteria:

- Surgically sterile
- Willing to abstain from sexual intercourse or use a reliable form of contraception (e.g. condom with spermicide), if having sex with a pregnant or non-pregnant woman of childbearing potential, from screening until 3 months after the final dose of IMP.
- Surgically sterilised or post-menopausal female partner or same-sex relationship

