2.1.3 Subject selection

The study is designed as a first in man study in patients with stable HBeAg-negative CHB who are otherwise healthy with no compromise in their liver function. The rationale for moving directly into patients with CHB, and not administering Vaccine FP-02.2 to healthy volunteers first, was based on the following points:

- Evaluating the safety of Vaccine FP-02.2, in the absence of HBV exposure i.e. in healthy volunteers will not adequately assess safety of the immune response generated to FP-02.2 in the context of existing HBV infection.
- Patients with CHB have, unlike 90% of the population, failed to clear the initial infection and the chronic exposure to HBV has a significant impact on the immune responsiveness to HBV antigens, compared to healthy non-infected subjects; therefore, the immune response to Vaccine FP-02.2 in patients is likely to be very different to the immune response to Vaccine FP-02.2 in healthy volunteers.

From these considerations, it was determined that assessing safety and immunogenicity of Vaccine FP-02.2 in healthy volunteers would be of limited value with the results likely to show a greater immune response generated to Vaccine FP-02.2 and not being able to assess the key safety variable i.e. the acute immune-toxicity in the presence of HBV infected liver cells. Therefore, it was determined that it is most appropriate to conduct this first in man study in stable patients chronically infected with HBV.

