- Bloods for assessing liver function will be taken at 7 days after each injection and prior to the subsequent injection. These results will be reviewed by the Principal Investigator (PI) for each site. Any subject experiencing an increase in alanine aminotransferase (ALT) to 10 times the upper limit of normal (ULN), a prothrombin time, reported as the international normalised ratio (INR) of more than 1.3 or a total bilirubin greater than 3 times the ULN, will be called back to study site for assessment and will not receive any more doses of Vaccine FP-02.2. Subjects with an ALT above 5 times the ULN will be closely monitored and dosed at the discretion of the Investigator.
- Any subject experiencing a flare with decreased liver function will be managed by the PI for the site, as per local clinical protocols.
- A safety review committee (SRC) (defined as the country CIs, if applicable, and the study medical monitors) will review and assess all safety data for Cohorts 1 and 2 after at least 15 or 30 subjects, respectively, have completed Day 36 assessments.

Communication between the sites to discuss subject safety is of critical importance and, in addition to the SRC. Sites are encouraged to contact the Sponsor's medical monitor or regional CIs for any questions or concerns about the study, especially if related to patient safety.

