6.2 Exclusion criteria

1. Liver disease other than CHB (a diagnosis of steatosis is permitted providing inclusion criterion 6 is met).
2. Evidence of Liver cirrhosis on Fibroscan at screening (Liver cirrhosis is defined as a Fibroscan measurement of >11.5 KPa), or previous history or evidence of cirrhosis on radiological imaging, Fibroscan or liver biopsy.
3. Positive serology for HIV-1 or HIV-2 or HCV or HDV antibodies.
4. Immunodeficient or autoimmune conditions due to disease or medication e.g. systemic steroids within previous 12 weeks. (Topical or inhaled steroids are permissible).
5. Clinically relevant co-morbidity, e.g. autoimmune disease.
6. Clinically relevant anaemia or leukopenia in the opinion of the investigator.
7. Cancer or treatment for cancer within 3 years prior to screening excluding basal cell carcinoma of the skin, which is allowed.
8. Known or suspected intolerance or hypersensitivity to the IMP or closely related compounds or any of the stated ingredients.
9. Receipt of any IMP within 90 days prior to screening or currently receiving IMP or intent to receive IMP.
10. Current substance or alcohol abuse that in the opinion of the Investigator would interfere with compliance or with interpretation of study results.
11. Any condition that in the opinion of the Investigator might interfere with study objectives.
12. Pregnant or breastfeeding.
13. Subjects should not have received, during the 6 month period prior to screening, any medications or other treatments that may adversely affect the immune system such as allergy injections, immunoglobulins, interferons, cytotoxic drugs or other drugs known to be frequently associated with significant major organ toxicity, or systemic corticosteroids (oral or injectable).
Immunosuppressive treatment such as azathioprine or mercaptopurine is not permitted in the 6 months prior to screening.
14. Administration of live vaccines (such as live influenza vaccinations or live travel vaccinations) from 10 days prior to the screening visit until Day 85.

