7.10.1 Possible reasons for discontinuing subjects from continued study treatment

Examples of possible reasons for premature withdrawal of subjects:

- Major protocol violations;
- Pregnancy;
- Serious intercurrent illness;
- AEs which, in the judgement of the PI or Co-Investigator and subject to discussion with the Sponsor's medical advisor, justifies discontinuation;
- Non-compliance with study requirements;
- Withdrawal of consent by the subject;
- Subjects experiencing clinically significant injection site reactions or clinically significant changes in haematology and serum biochemistry results, considered possibly related to administration of the IMP, after a dose may not receive the subsequent dose of medication, at the discretion of the PI, in discussion with the Chief Investigator (CI) or the Sponsor's medical advisor. However, safety, virology and immunogenicity data will continue to be collected until the end of the study unless the subject withdraws his/her consent.

If a subject is withdrawn from study treatment, relevant study procedures e.g. physical examination, clinical laboratory analyses for safety and immunogenicity will be performed wherever possible. The reason(s) for discontinuation will be recorded in the appropriate section of the eCRF. Any subject who prematurely terminates participation and who has received at least one injection of the study treatment will undergo relevant post-study procedures for reasons of medical prudence, including a final examination and safety laboratory studies, unless the subject has withdrawn his/her consent and refuses to be examined and/or have blood drawn.

If a subject terminates participation due to an AE possibly related to the study medication or study procedures, the subject should be followed up by additional examinations according to the medical judgment of the Investigator until the abnormal condition is resolved or the Investigator deems further observations or examinations to be no longer medically indicated. If the subject refuses to be followed up the Investigator should explain the importance of the follow-up and encourage the subject to allow follow up. Subjects who elect to discontinue dosing should be encouraged to continue with other study procedures until the end of study if they are willing.

Study stopping rules

Individual subjects

An individual subject will have treatment discontinued if he/she experiences any one or more of the following events:

- ALT \geq 10 times the ULN

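### Inclusion criterion 6 joins ALT and AST with *or*, so a subject can enter on one enzyme while the other exceeds 1.5 x ULN, and no other criterion sets a numeric limit on either

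*Protocol*

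**What the plan says.** Protocol section 6.1, criterion 6, is the only eligibility criterion with a transaminase figure: "ALT or AST \leq 1.5 x the ULN via the local laboratory at the Screening Visit".

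Three other places bear on how it should be read:

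- Section 2.1.3 (Subject selection) describes stable HBeAg-negative patients "who are otherwise healthy with no compromise in their liver function".
- Section 6.2, exclusion 1, removes liver disease other than chronic hepatitis B but makes an exception: "a diagnosis of steatosis is permitted providing inclusion criterion 6 is met".
- Section 6.2, exclusion 11, is a general clause left to judgement: "Any condition that in the opinion of the Investigator might interfere with study objectives". It names no enzyme and no level.

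Two ALT levels apply once a subject is on study. Section 2.1.4 says "Subjects with an ALT above 5 times the ULN will be closely monitored and dosed at the discretion of the Investigator". Section 7.10.1 says "An individual subject will have treatment discontinued if he/she experiences any one or more of the following events", and the first event listed is "ALT \geq 10 times the ULN". AST appears in neither rule.

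The flow chart (Table 1) schedules safety laboratory tests at screening and next at Day 8. The Visit 1 list in section 7.6.3 has an eligibility review but no safety laboratory test.

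**The concern.** An inclusion criterion has to be satisfied. When two conditions in it are joined by *or*, satisfying one is enough. A subject with AST at 1.4 x ULN and ALT at 3 x ULN therefore meets criterion 6 as written. So does a subject with the two enzymes reversed. The more natural clinical intention, that neither enzyme should exceed the limit, is not what the sentence says.

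This matters more here than in most trials. Sections 2.1.2 and 2.1.4 name immune-mediated death of infected hepatocytes, and the flare that could follow, as the theoretical risk of this first-in-man vaccine. Liver enzymes are a primary safety outcome. A subject who enters with one raised enzyme makes a later rise harder to interpret in arms of about 10. Sites in a multi-national trial may also read the conjunction differently and so enrol different populations under one protocol.

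The steatosis exception is the most concrete route. Exclusion 1 relies on criterion 6 as its safeguard, and a steatosis patient with raised ALT can satisfy that safeguard on AST alone.

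**Working it through.** The plan has no figure of its own to reproduce on this point. The check is logical, followed by simple ratios of thresholds.

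**1. Criterion 6 as written.** It reads: (ALT ≤ 1.5 x ULN) or (AST ≤ 1.5 x ULN).

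| ALT | AST | As written | If both must comply |
|---|---|---|---|
| ≤ 1.5 | ≤ 1.5 | admitted | admitted |
| > 1.5 | ≤ 1.5 | admitted | not admitted |
| ≤ 1.5 | > 1.5 | admitted | not admitted |
| > 1.5 | > 1.5 | not admitted | not admitted |

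The two readings differ in the middle two rows. In those rows criterion 6 sets no upper bound on the other enzyme.

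**2. Other numeric limits.** I went through every criterion in sections 6.1 and 6.2. There are figures for age, duration of infection and treatment, HBV DNA, Fibroscan and several time windows. None applies to ALT or AST. Exclusions 5 and 11 rest on judgement. Exclusion 1 refers back to criterion 6.

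**3. Whether a later scheduled test catches it before dose 1.** Table 1 places safety laboratory tests at screening and Days 8, 29, 36, 57, 64, 85 and 225, which is 8 occasions. Table 6 in section 7.11.5 budgets 8 serum biochemistry samples, so the two agree and leave no Day 1 sample. Criterion 6 is itself tied to the Screening Visit. The screening value is thus the only scheduled enzyme result before the first injection. Under SAP section 8.1 it will also be the laboratory baseline unless an unscheduled sample was taken. Both enzymes are in the safety panel (Table 5), so the information needed to apply either reading is available.

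**4. Distance to the on-study ALT levels.** Fold rise = on-study level ÷ entry level.

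- From 1.5 to 10 x ULN: 10 / 1.5 = 6.7-fold.
- From 1.5 to 5 x ULN: 5 / 1.5 = 3.3-fold.
- From 5 to 10 x ULN, for a subject admitted on AST alone with ALT at 5 x ULN: 10 / 5 = 2-fold.

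This runs one way only. The on-study rules name ALT and not AST, so the distance shortens only when AST is the enzyme that qualified the subject.

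**5. What cannot be computed.** The number of subjects affected depends on how often one enzyme exceeds 1.5 x ULN while the other does not, and on how each site reads the criterion. The documents give neither. The ratios in step 4 compare thresholds and do not estimate impact.

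**The case against.** The strongest reply is that criterion 6 does not work alone. Subjects need at least 2 years on entecavir or tenofovir, a stable dose for 6 months, and HBV DNA below 50 IU/mL for at least 12 months. Other liver disease, cirrhosis, HCV, HDV, relevant co-morbidity and interfering alcohol abuse are excluded. The investigator signs each laboratory report (section 7.6.1.2), may repeat tests at discretion (section 7.11.1) and reviews eligibility again on Day 1. All of this stands. It makes gross elevation at entry unlikely, and a reader who inferred that the second enzyme may be raised without any limit would go too far. What is missing is a numeric limit. The safeguards that remain depend on judgement, name neither enzyme, and may be applied differently across sites.

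Three other strong inferences are tempting, and the documents do not support them.

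- *The entry rule contradicts the 5 x and 10 x ULN rules.* Those rules govern events and increases on study. An entry limit and an on-treatment limit may differ without contradiction. ALT at 10 x ULN with AST at or below 1.5 x ULN would also be an extreme discordance, for which no frequency is given.
- *One such subject, being 10% of an arm, threatens the study-wide stop.* That rule in section 7.10.1 is 20% or more of subjects, not of an arm. One subject is 1/60 = 1.7% of the planned total or 1/15 = 6.7% of Cohort 1; 20% would be 12 or 3 subjects. The rule does not define its denominator, but that is a separate matter.
- *ALT rises in these subjects could not be attributed.* The trial has randomised placebo and IC31-alone controls, and SAP section 12.6.3 provides change-from-baseline summaries. Interpretation becomes harder, not impossible. One part of the worry remains: the shift tables use only low, normal and high, so a move from 3 x to 8 x ULN would read as high to high.

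**Conclusion.** The concern holds in a limited form. As written, criterion 6 admits a subject with one enzyme above 1.5 x ULN, and no other criterion sets a figure for that enzyme. This is in tension with the population described in section 2.1.3, weakens the steatosis condition in exclusion 1, and leaves room for sites to apply different entry rules. No scheduled enzyme test follows screening before dose 1.

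The demonstrable size is the shorter distance to the on-study ALT level: 2-fold from 5 x ULN against 6.7-fold from the 1.5 x ULN limit, and only for subjects who qualified on AST. The number of subjects affected is unknown.

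The conclusion rests on the literal reading of *or*. If every site already reads the criterion as requiring that neither enzyme exceed the limit, no one is wrongly admitted and only the wording needs repair. Because the wording decides who may be dosed in a trial whose named risk is liver flare, this is more than a clerical slip.

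**What to change.** Reconcile criterion 6 with section 2.1.3 and exclusion 1 by stating explicitly whether both enzymes must meet the existing limit. Requiring ALT and AST both to be at or below 1.5 x ULN at screening would agree with section 2.1.3, keep the present figure, and carry through to the steatosis exception without further change. If the sponsor does intend either enzyme to suffice, the protocol should say so and explain how that fits section 2.1.3.

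Align the eCRF eligibility check with the clarified wording.

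For subjects already enrolled, list at the blinded data review (SAP section 11.3) anyone with either screening enzyme above 1.5 x ULN, with both values. This needs no new data, and it shows whether the issue arose in practice. If recruitment has ended, this listing is the part that still matters.

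The cost is perhaps a few more screen failures and a protocol amendment, which may count as substantial under section 13.10 and then needs competent authority approval and a favourable ethics opinion. SAP section 13.1 records 15 subjects enrolled in Cohort 1 before the transition on 30 November 2016, and placebo subjects are pooled over Cohorts 1 and 2. A change between cohorts could therefore pool controls recruited under different entry rules, so the study report should state which subjects entered under which wording.

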6.2 Exclusion criteria

1. Liver disease other than CHB (a diagnosis of steatosis is permitted providing inclusion criterion 6 is met).
2. Evidence of Liver cirrhosis on Fibroscan at screening (Liver cirrhosis is defined as a Fibroscan measurement of >11.5 KPa), or previous history or evidence of cirrhosis on radiological imaging, Fibroscan or liver biopsy.
3. Positive serology for HIV-1 or HIV-2 or HCV or HDV antibodies.
4. Immunodeficient or autoimmune conditions due to disease or medication e.g. systemic steroids within previous 12 weeks. (Topical or inhaled steroids are permissible).
5. Clinically relevant co-morbidity, e.g. autoimmune disease.
6. Clinically relevant anaemia or leukopenia in the opinion of the investigator.
7. Cancer or treatment for cancer within 3 years prior to screening excluding basal cell carcinoma of the skin, which is allowed.
8. Known or suspected intolerance or hypersensitivity to the IMP or closely related compounds or any of the stated ingredients.
9. Receipt of any IMP within 90 days prior to screening or currently receiving IMP or intent to receive IMP.
10. Current substance or alcohol abuse that in the opinion of the Investigator would interfere with compliance or with interpretation of study results.
11. Any condition that in the opinion of the Investigator might interfere with study objectives.
12. Pregnant or breastfeeding.
13. Subjects should not have received, during the 6 month period prior to screening, any medications or other treatments that may adversely affect the immune system such as allergy injections, immunoglobulins, interferons, cytotoxic drugs or other drugs known to be frequently associated with significant major organ toxicity, or systemic corticosteroids (oral or injectable).
Immunosuppressive treatment such as azathioprine or mercaptopurine is not permitted in the 6 months prior to screening.
14. Administration of live vaccines (such as live influenza vaccinations or live travel vaccinations) from 10 days prior to the screening visit until Day 85.

